10.4 Statistical Analysis Plan

10.4.1 Quantitative Data Analysis

The primary analyses will estimate the effect of the three conditions and two hypothetical trial types on adolescent WTP scores and parent WTS scores. All analyses will be performed separately for adolescents and parents. The type I error rate will be set to $\alpha = 0.05$ separately for adolescent-specific and parent-specific hypothesis tests.

Linear mixed models will be used to estimate the effect of the three consent conditions and two trial types on WTP and WTS scores, with a random participant effect (i.e. random intercept) to account for the potential correlation between the multiple responses per participant. Aside from consent condition and trial type effects, the LMMs will also include adolescent's sex assigned at birth and study site as fixed effects.

Heterogeneity of consent condition and trial type effects across study sites will be evaluated. If statistically significant interactions occur ($p<0.05$), site-specific estimates of effects will be presented to supplement the pre-planned analyses. P-values from pairwise comparisons of consent condition effects will be adjusted for multiple comparisons to control the type I error rate at the level $\alpha=0.05$ separately for parents and adolescents. Tests of trial type effects will be performed at the level $\alpha=0.05$ separately for adolescents and parents and separately from tests of consent condition effects.

As a secondary sensitivity analysis, we will evaluate whether concern about HIV, family context (frequency of communication, connectedness), and other demographic and socioeconomic factors affect WTP/WTS participation in biomedical research. We will examine these effects by adding variables into the models to determine if they moderate the relationship between consent condition and WTP/WTS scores.

Although WTS and WTP scores are discrete, it is common to analyze these data using linear models. Research suggests that this approach is robust to the discrete nature of the data if the normality assumption is not severely violated. However, usage of the LMM may be problematic if a large number of responses occur on the boundary (e.g. a high proportion of 1's or 5's). In this case we will fit a linear quantile mixed model for the median WTP and WTS scores, which does not require normality.³⁴

The primary endpoint analyses will be based on the observed data. By study design requirement, it will not be possible for sex assigned at birth to be missing and so no methods for missing covariates are needed for the primary analyses. If a key demographic or socioeconomic measures are missing in more than 5% of participants, the secondary sensitivity analyses described above will utilize multiple imputation by chained equations for those analyses.³⁵

The effect of the three conditions on the mean adolescent UBACC scores will be estimated using linear mixed-effect models (LMMs) that include a random participant effect (i.e. random intercept) to account for correlation between the multiple UBACC assessments per participant. Aside from consent condition and trial type effects, the LMMs will also include adolescent's sex assigned at birth and study site as fixed effects.

The effect of the trial type on the mean parent UBACC scores will be estimated using LMMs that include a random participant effect (i.e. random intercept) to account for correlation between the multiple UBACC assessments per participant. Aside from trial type effects, the LMMs will also include adolescent's sex assigned at birth and study site as fixed effects.

Using the same strategy described in Section 6.1 (e.g., to evaluate how demographic factors affect WTP/WTS participation), we will perform analyses that evaluate the extent to which capacity to consent, as measured by the UBACC, influences WTP/WTS scores.

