5.2 Randomization Procedures

5.2.1. Adolescent Participants

Adolescents will be randomized in a 1:1:1 ratio into 1 of the 3 consent conditions using block randomization with block size k=3 (so that in every 3 subjects, exactly 1 is allocated to each condition). The randomization will be stratified by study site and sex assigned at birth. Within study site, sex assigned at birth, and consent condition, the order in which the hypothetical trials will be presented to adolescents will be block randomized with block size k=2.

A subset of 6-8 adolescents (3-4 of both sexes) at each site will be selected using quota sampling for participation in the debriefing interview. Participants will be asked if they are willing to participate in the debriefing interview unless the quota for their demographic group has been reached.

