5.2.2. Parent Participants

Enrollment of parents will be restricted to approximately 18 parents of adolescent natal males and 18 parents of natal adolescent females at each study site. Parents will indicate the acceptability of each of the three consent conditions for each of the two hypothetical trials. Independently of the gender strata, the order of hypothetical trial presentation will be block randomized with blocks size k=2. Separately for each hypothetical trial, the order of evaluation for the three consent conditions will be randomized so that each ordering is equally likely.

A subset of 6-8 parents at each site will be selected using quota sampling for participation in the debriefing interview. Participants will be asked if they are willing to participate in the debriefing interview unless the quota for their demographic group has been reached.

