10.0 STATISTICAL AND ANALYTIC CONSIDERATIONS

10.1 Study Design

This study will use a quasi-experimental design to explore how the informed consent process affects the acceptability of biomedical HIV prevention trials, from the perspective of behaviorally high-risk minor adolescents and the parents of minor adolescents.

Adolescent participants will undergo a simulated consent process for each of two hypothetical studies based on their randomized consent condition. Hypothetical Study 1, modeled after ATN 113, is an open-label study of oral TDF-FTC and hypothetical Study 2, modeled after HPTN 077,

is a Phase IIa trial of an injectable HIV integrase inhibitor. After completing the simulated consent process for the first hypothetical study, the adolescent will complete a CASI assessing the adolescents' WTP and will work with RS to complete the UCSD Brief Assessment of Capacity to Consent (UBACC).²⁸ The simulated consent process and follow-up assessments will then be completed for the second hypothetical study. The presentation order for the two hypothetical studies will be randomly determined (see Section 3.3 for more details on the randomization procedure).

Parent participants will review all three consent conditions for each of the two hypothetical studies and complete a CASI assessing the acceptability of the three approaches to consent. The presentation order of the hypothetical studies and the review order for the consent conditions for each hypothetical study will be randomly determined (see Section 3.3. for more details on the randomization procedure).

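### Trial order and vignette order are randomised but have no term in the mixed models, so within-person tests lose some power if ratings shift with order

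*Combined protocol and SAP*

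**What the plan says.** Sections 3.3 and 5.2 randomise order at two levels.

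- **Trial order, adolescents (5.2.1).** Within site, sex and consent condition, "the order in which the hypothetical trials will be presented to adolescents will be block randomized with block size k=2".
- **Trial order, parents (5.2.2).** "the order of hypothetical trial presentation will be block randomized with blocks size k=2".
- **Vignette order, parents (5.2.2).** Separately for each trial, "the order of evaluation for the three consent conditions will be randomized so that each ordering is equally likely". No blocking is mentioned. Section 10.1 repeats that "the review order for the consent conditions for each hypothetical study will be randomly determined".

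Section 3.0 gives protection against ordering bias as the reason for varying order.

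Section 10.4.1 then lists the model terms for willingness to participate (WTP) and willingness to support (WTS): "Aside from consent condition and trial type effects, the LMMs will also include" sex assigned at birth and site, with a random participant intercept. The same list serves the adolescent capacity-to-consent (UBACC) model. For parents, "The effect of the trial type on the mean parent UBACC scores will be estimated using LMMs", and "Aside from trial type effects, the LMMs will also include" sex and site again.

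Trial type is tested formally: "Tests of trial type effects will be performed at the level" 0.05, separately in each group. No period, sequence or position term appears anywhere in section 10. The secondary analyses add only concern about HIV, family context, demographic and socioeconomic factors, and UBACC.

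**The concern.** Each participant goes through a consent process, a rating and a UBACC, then repeats all three in the same sitting. Parents give six vignette ratings. Learning, fatigue or anchoring could plausibly move scores with order. The design allows for this and the analysis does not.

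If scores do shift, the shift stays in the within-person residual. Three sets of tests are exposed:

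- Aim 3, trial type, in both groups.
- Aim 2, the parent consent-condition contrasts.
- The parent UBACC comparison between trials.

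Aim 1 is not exposed, nor is adolescent UBACC by condition. Those comparisons are between adolescents, and each adolescent's mean contains both periods.

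**Working it through.** **The plan's own power figure.** Section 10.3 claims 80% power at f² = 0.09 with 120 adolescents and 7 predictors. The listed terms account for all seven: 2 for condition, 1 for trial type, 1 for sex, 3 for site. A noncentral F test with 2 and 112 df and noncentrality 0.09 × 115 = 10.35 gives 81.8%, close to the stated figure. It covers only the adolescent consent-condition test, which order does not affect. No power is given for trial type.

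**Inputs.** n = 144 per group (section 3.2) and two-sided alpha 0.05 (10.4.1; two-sided is assumed). The documents give no residual SD, within-person correlation or order effect. Shifts are therefore in units of the within-person residual SD, s = 1: *p* is the first-to-second trial shift and *D* the first-to-last vignette shift, taken as linear. The 80% starting power is illustrative (1.96 + 0.84 = 2.80).

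**Adolescent trial type, two scores each.** The within-person difference is the trial effect ± *p*, with error variance 2. Blocking cancels *p* from the mean, so the true variance is 2/n. Without a period term the reported variance is (2 + *p*²)/n. Hence:

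- SE factor = √(1 + *p*²/2)
- power = Φ(2.80 − 1.96 × SE factor)

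| *p* | Reported SE | Power | Detectable difference |
|---|---|---|---|
| 0 | – | 80% | 0.330 s |
| 0.25 | +1.6% | 79% | 0.334 s |
| 0.5 | +6.1% | 77% | 0.344 s |
| 1.0 | +22% | 66% | 0.382 s |

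The same SE factor applies to parent UBACC. In rating points, with s assumed between 0.6 and 1.0, a 0.3-point shift inflates the SE by 2% to 6% and a 0.5-point shift by 6% to 16%.

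**Parent ratings, six each, five within-person df.** A period shift adds 6 × (*p*/2)² = 1.5*p*² to the within-person sum of squares. A linear position shift adds 2 × 2 × (*D*/2)² = *D*². The reported variance factor is therefore 1 + (1.5*p*² + *D*²)/5.

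*Period shift alone.* The true variance is unchanged. For *p* = 0.25, 0.5 and 1.0 the reported SE of both trial type and the consent contrasts rises 0.9%, 3.7% and 14%; power is 79%, 78% and 71%.

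*Position shift alone, consent contrast.* With unblocked order the mean squared position difference between two vignettes is (*D*²/4 + *D*²/4 + *D*²)/3 = *D*²/2, against error variance 2 per trial. The true variance factor is 1 + *D*²/4. Power = Φ[(2.80 − 1.96√(1 + *D*²/5)) / √(1 + *D*²/4)].

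| *D* | True SE | Reported SE | Type I error | Power |
|---|---|---|---|---|
| 0.25 | +0.8% | +0.6% | 5.0% | 79% |
| 0.5 | +3.1% | +2.5% | 5.1% | 78% |
| 1.0 | +11.8% | +9.5% | 5.5% | 72% |

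With a Bonferroni test of three pairs the last figure is 71%. The baseline SE is √(1/144) = 0.083 s. The detectable difference rises from 0.233 s to 0.257 s at *D* = 1.0, which is 0.012 to 0.024 rating points if s is 0.5 to 1.0 points.

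*Position shift alone, parent trial type.* Each trial contains all three positions, so only the reported SE is affected: +9.5% and 74% power at *D* = 1.0.

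**Simulation check** (within-person least squares, equivalent to the random-intercept model for these contrasts in complete data; blocked trial order, unblocked vignette order):

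| Test and shift | Power, term omitted | Power, term fitted |
|---|---|---|
| Adolescent trial type, *p* = 1 | 64% | 79% |
| Parent consent contrast, *p* = 1 | 72% | 80% |
| Parent consent contrast, *D* = 1 | 72% | 79% |
| Parent consent contrast, *p* = *D* = 1 | 64% | 80% |

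In the first row the reported SE is 0.144 against a true SD of 0.118. The formula's 66% is slightly optimistic because it uses normal quantiles. Estimates were unbiased, and with no order effect the extra terms cost essentially nothing.

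**The case against.** The strongest case against the point is that nothing here is an error. Estimates are unbiased, the purpose given in section 3.0 is met, and the one test with a numerical power target is untouched. For trial type the omission makes the test conservative, which is the safe direction. All of this stands.

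Every power figure also depends on assumed shifts and on effects sitting exactly at 80% power. If parents' consent means were evenly spaced at f² = 0.09, with s taken as the full residual SD, the extreme pair would differ by about 0.73 SD and adjacent pairs by about 0.37 SD. At *D* = 1.0, extreme-pair power would stay above 99.9%, and unadjusted adjacent-pair power would go from 99.3% to 97.8%. The drop to 72% therefore describes a much smaller effect, about a third of that extreme-pair difference. This also stands. Section 10.3 says parents' tests can detect something smaller than f² = 0.09 but never says how small, so the loss for this study cannot be fixed.

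The parent sample is itself unclear: section 3.3 implies 15 + 15 per site (120) and section 5.2.2 implies 18 + 18 (144). At 120 the detectable consent difference is already 0.256 s with no order effect, so that discrepancy matters about as much as the worst case shown here. The SE percentages do not depend on n.

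Finally, a position main effect would not capture a contrast effect that depends on which vignette came first. That is true, but it does not make the simpler term less useful.

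**Conclusion.** The concern holds, at low severity. Order is randomised and is absent from every model in section 10.4.1. The consequence is a possible loss of power for trial type in both groups, for the parent consent-condition contrasts and for parent UBACC by trial.

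Two mechanisms should be kept apart. With blocked trial order, the reported SE is too large and the test conservative. With unblocked vignette order, the parent consent contrasts carry real extra variance, which the reported SE roughly tracks, falling slightly short.

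The loss is about one power point at a shift of 0.25 residual SD and becomes material only near one residual SD. These sizes rest on assumed shifts, an assumed residual SD, additive order effects and an illustrative 80% starting point. No conclusion of the study is shown to change.

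**What to change.** In section 10.4.1:

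1. Add presentation period (first or second trial) as a fixed effect in the adolescent WTP model, the parent WTS model and both UBACC models.
2. Add vignette position (1, 2, 3, categorical) as a fixed effect in the parent WTS model.
3. Define both from the order assigned at randomisation.
4. State that the Qualtrics export keeps the vignette order shown to each parent for each trial.

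The cost is a few lines of SAP wording and 1 df in the adolescent and parent UBACC models, or 3 df in the parent WTS model. No section says that vignette order is stored for each parent, so this needs checking. If it is not kept, the period term can still be added alone.

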Potential participants will be recruited from clinical settings and HIV testing centers, or self-screen online. Potential participants will take a short CASI screening survey to determine eligibility. All eligible participants will provide contact information to establish a study visit appointment. Those eligible and screening in-person will either participate on the same day as the screening, or, if unable to stay, they will be contacted to establish a study visit appointment. Eligible participants who screen online will also provide their contact information to establish a study visit appointment.

Study participants will attend an in-person session at their respective AMTU. During the session, they will complete a CASI that collects demographic, social, behavioral, and attitudinal measures.

All study participants will undergo a simulated consent process for each of two hypothetical studies modeled after ATN 113 and HPTN 077. Procedures are slightly different for parents than for adolescents, so each group is described separately below:

Adolescent Participants: First, the adolescent participant will complete a demographic CASI. *For each hypothetical trial*, RS will lead the participant through a simulated consent process consistent with their randomized consent condition. Then, the participant will complete a CASI assessing WTP and will work with RS to complete the UCSD Brief Assessment of Capacity to Consent (UBACC). After the second UBACC, the adolescent will complete overall WTP, medical mistrust, and end of study questions.

Parent Participants: *For each hypothetical trial*, RS will review the informed consent forms with the parent. The parent will complete a CASI with three vignettes that describe each of the three possible consent conditions. Parents will rate the acceptability of each vignette. Then, the participant will work with RS to complete the UCSD Brief Assessment of Capacity to Consent (UBACC). After the second UBACC, the participant will answer demographic questions, medical mistrust, and end of study questions.

A subset of 6-8 adolescents and 6-8 parents per study site will complete a debriefing interview assessing adolescent and parent perspectives on the various consent conditions in greater depth, and to better understand the role of study features, family, and adolescent characteristics in willingness to

participate/willingness to support the hypothetical research studies.

MONITORING:

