6.2 Enrollment/Entry

RS will prepare the participant to complete demographic, social, and attitudinal measures by CASI. Adolescent participants will complete these measures in two parts. The beginning CASI will include demographic information, SES, parental monitoring, and concern about HIV and the final CASI will include overall WTP, medical mistrust, and closing questions. Parent participants

will complete demographics, SES, WTS, concern about HIV, medical mistrust, and closing questions during the final CASI. The measures are summarized in **Table 2**, below.

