6.2.1 Quantitative Evaluations

Table 2: Quantitative Measures

Demographics	Scale	Description of Items included
Demographics		Age, race/ethnicity, sexual orientation, gender identity, education, employment, health insurance status, city, living situation
Socioeconomic Status	FAS-III ^{26 27} (Adolescents)	7- questions adapted from the Family Affluence Scale-III, measuring a family's financial status based off of number of vehicles, computers, bathrooms, adolescent having their own bedroom, if the family has a dishwasher, number of times traveled outside US, and overall perception of family's financial status.
Social Support	MSPSS- modified ²⁸	4 –Likert questions on a 7-point scale ranging from very strongly disagree to very strongly agree, measuring parental support and relationships with adolescents.
Parental Monitoring	Parental knowledge - modified ²⁹ (Adolescents & Parents)	5- point Likert scale measuring parental knowledge, disclosure, solicitation, and parental control. The scale has 25 statements for the (adolescent/parent) Strongly Disagree to Strongly Agree for each statement. Adolescent statements such as “My parent(s) know what I do during my free time. Parent statements such as “I know what my teen does during his/her free time.”
Medical Mistrust ³⁰	(Adolescents & Parents)	6, 5-point Likert items that measure the degree to which the participant trusts medical researchers.
Communication	Communication with Parents ³¹ (Adolescents & Parents)	5 Questions asking the number of times parents and adolescents have communicated about relationships, sex, sexually transmitted infections (HPV, HIV), same sex relationships, and using a condom. Answers range from Never, Once/twice, Many times, and Don't know
Concern about HIV	HIV Risk perception ³² Adolescents & Parents	2, 5-point Likert questions about adolescent worry of being infected with HIV/AIDS and parents worry of their adolescent being infected with HIV/AIDS.
Sexual Behavior	Sexual Behavior ³³ (Adolescents)	5 questions for adolescents regarding sexual intercourse partners.
Capacity to Consent	UBACC ²⁵	8 open-ended questions (answers scored 0-2) to measure participant's understanding of research design, risks & benefits, voluntariness
Acceptability	Willingness to Participate ³³ (Adolescents)	3 Likert-type items that begin with question stems such as “If offered a chance to participate in this study, how likely are you to participate...”

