10.3 Sample Size and Power Estimates

This study is powered to detect a meaningful difference in adolescent WTP scores and to detect a meaningful difference in parental WTS scores between the three consent conditions being studied. The WTP scores will be estimated as the mean score of three 5-point Likert scales. Based on the assumption that adolescent WTP scores are normally distributed and analyses using a linear regression model based on 120 participants (40 per consent condition) and with 7 independent variables in the model will provide 80% power to detect a $0.09 f^2$ effect size, which is between a small ($f^2=0.02$) and a medium effect size ($f^2=0.15$), for consent conditions. This power calculation, which assumed a single observation per participant, is conservative and the actual study which will have two observations per participant (one for each simulated consent process) will have a larger statistical power to detect an $f^2=0.09$ effect size for consent condition. Since the test of consent condition effects based on parental WTS scores is a within-participant comparison rather than an across-participant comparison, a test of parental consent condition effects will have 80% power to detect an even smaller effect size (f^2) compared to tests for consent condition effects using adolescent WTP scores.

A subset of 24–32 (6–8 per study site) adolescents and 24–32 (6–8 per study site) parent participants will be selected to participate in the debriefing interview. Prior research with similar populations suggest that this sample size is sufficient for eliciting a variety of perspectives and establishing key themes in the data.

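### The adolescent primary model adjusts only for sex and site; prespecifying age and concern about HIV, both collected before the simulated consents, would probably add modest precision at low cost

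*Combined protocol and SAP*

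**What the plan says.** Section 10.4.1 specifies a linear mixed model with consent condition, trial type and a random participant intercept, and adds that "the LMMs will also include adolescent's sex assigned at birth and study site as fixed effects". The 5% type I error rate is set "separately for adolescent-specific and parent-specific hypothesis tests".

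Several other adolescent variables exist before exposure. The Study Abstract gives the order of the visit: "First, the adolescent participant will complete a demographic CASI", and the simulated consents follow. Section 6.2 says of adolescents: "The beginning CASI will include demographic information, SES, parental monitoring, and concern about HIV". Table 2 lists the demographics as "Age, race/ethnicity, sexual orientation, gender identity, education, employment, health insurance status, city, living situation". Medical mistrust comes in the final CASI, and the UBACC is given after each simulated consent.

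Section 10.4.1 brings in concern about HIV, family context (communication and connectedness) and other demographic and socioeconomic factors only in a secondary sensitivity analysis. There the question is whether they affect willingness scores or moderate the consent effect. Sections 10.4.1 and 10.5 both state that the primary analysis needs no method for missing covariates, because sex assigned at birth cannot be missing.

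Section 10.3 bases power on a "linear regression model based on 120 participants (40 per consent condition") "with 7 independent variables in the model will provide 80% power to detect a" f² of 0.09 for consent condition. It counts one observation per participant and notes that the actual two will give "larger statistical power to detect an $f^2=0.09$ effect size for consent condition". Section 3.2 plans about 144 adolescents.

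**The concern.** Aim 1 compares three separate randomised groups, about 144/3 = 48 adolescents each. Stable differences between adolescents in their readiness to join a trial go into the standard error of every consent contrast. The second WTP score does not average them away. Baseline variables that predict WTP can remove part of this variation. In a linear model, adjusting for pre-exposure covariates in a randomised comparison leaves the meaning of the contrast unchanged.

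The planned secondary analysis does not do this job. A moderation question does not sharpen the primary contrast.

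Precision is scarcest in the adjacent comparisons. The Aim 1 hypothesis is an ordering (self-consent, then adult permission, then required parental permission), and 10.4.1 adjusts the pairwise p-values for multiplicity. Section 10.3 gives power only for the overall consent effect. Parents rate all three conditions themselves, so their consent contrast is within participant and the point does not extend to them.

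**Working it through.** **1. The plan's own figure.** Inputs from 10.3: N=120, 7 predictors, f²=0.09. Consent condition has u=2 degrees of freedom, v = 120−7−1 = 112, α=0.05. With Cohen's noncentrality λ = f²(u+v+1) = 0.09×115 = 10.35, the noncentral F gives power 0.818, and the smallest f² with 80% power is 0.086, which rounds to 0.09. The stated power holds.

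**2. Adding three 1-df covariates (10 predictors).** Let R² be the share of residual variance they explain. The documents give no value, so a range is assumed. The effect size becomes f²/(1−R²), and u+v+1 falls by 3.

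| Assumed R² | SE multiplier √(1−R²) | Power, N=120 | Power, N=144 |
|---|---|---|---|
| not adjusted | 1 | 0.818 | 0.890 |
| 0 | 1 | 0.807 | 0.882 |
| 5% | 0.975 | 0.828 | 0.899 |
| 10% | 0.949 | 0.849 | 0.914 |
| 20% | 0.894 | 0.890 | 0.943 |

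Example at N=144, R²=10%: λ = (0.09/0.90)×136 = 13.6, power 0.914. Break-even is about R² = 3/115 = 2.6% at N=120 and 3/139 = 2.2% at N=144.

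**3. Adjacent pairs, one observation, N=144.** Assume equal spacing, with condition means −d, 0, +d in SD units. Then f² = 2d²/3, so d = √(1.5×0.09) = 0.367. SE = √(2/48) = 0.204, and 0.367/0.204 = 1.80. Assume Tukey adjustment, since the plan names no method; the critical value is about 2.37. Power is 29%, and 30%, 32% or 36% at R² of 5%, 10% or 20%. For the extreme pair (gap 0.735, ratio 3.60) it is already 89%.

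**4. Adjacent pairs, two observations, N=144.** This is closer to the planned model. Let ρ be the within-participant correlation (assumed; not in the documents). The variance of a participant's mean is ρ+(1−ρ)/2. Covariates that explain a share R² of between-participant variance reduce it to ρ(1−R²)+(1−ρ)/2. At ρ=0.5:

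| R² (between-participant) | Variance | SE = √(2×variance/48) | Adjacent-pair power |
|---|---|---|---|
| not adjusted | 0.750 | 0.177 | 39% |
| 5% | 0.725 | 0.174 | 40% |
| 10% | 0.700 | 0.171 | 42% |
| 20% | 0.650 | 0.165 | 45% |

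The same formula gives 34% unadjusted at ρ=0.7 (variance 0.85) and 45% at ρ=0.3 (variance 0.65).

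**5. Overall test, two observations, N=144, unadjusted.** λ = 0.09×139/variance = 14.7, 16.7 and 19.2 at ρ = 0.7, 0.5 and 0.3, which gives power of about 0.93, 0.96 and 0.98.

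**The case against.** The strongest reply is that nothing here is wrong. Consent condition is randomised within site and sex, and the model contains exactly those two factors. A reader might infer that leaving out the other covariates biases the contrast or undermines the stated power. The documents do not support that: randomisation protects the contrast, and the 80% reproduces.

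A reader might also take the precision as free. It is not. If the covariates explain nothing, about one power point is lost, and below roughly 2–3% of variance there is no gain. Low values cannot be ruled out in a sample restricted to ages 14–17 with recent high-risk sexual activity. Participants may decline questions, so a missing-value rule becomes necessary.

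Nor does the plan assert that these variables predict WTP. It says only that this will be evaluated. Its description of family context does not name parental monitoring, and Table 2 lists 25 monitoring statements over four domains without a single-score rule.

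The 29% adjacent-pair figure should not be read as the power of the planned analysis, because it ignores the second observation. With two observations the overall test already has high power, and the extreme pair is well covered even with one.

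Finally, 10.4.1 falls back on a median mixed model if responses pile up at 1 or 5. There, adding covariates can change what the contrast means.

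All of this stands, and it limits the size of the point. It does not remove it: the variables are already collected before exposure, and no planned analysis uses them to sharpen the primary contrast.

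**Conclusion.** The point holds as a low-cost improvement in precision for adolescents, not as the correction of an error. If the covariates explain 5–20% of variance, overall power at N=144 with one observation rises by about 1 to 5 points. Adjacent-pair power with two observations at ρ=0.5 rises by about 1 to 6 points. If they explain nothing, overall power falls by about 1 point.

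These sizes rest on f²=0.09 from 10.3 and on assumed values for R², ρ, equal spacing and Tukey adjustment. Even after adjustment, adjacent-pair power stays below 50% at ρ=0.5, so covariates alone will not secure the hypothesised ordering. The claim that the contrast keeps its meaning applies to the linear mixed model, and not automatically to the median fallback.

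**What to change.** Before outcome data are examined, amend the SAP as follows.

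- **10.4.1, adolescent primary model:** add age and the concern-about-HIV score as fixed effects. Add parental monitoring only if a scoring rule is stated.
- **Missing baseline values:** fill them in a way that ignores arm, for example with the overall adolescent mean, so that nobody is dropped. Revise the statements in 10.4.1 and 10.5 that no missing-covariate method is needed. Say how this rule sits beside the chained-equations imputation planned for the secondary analyses.
- **Supporting analysis:** keep the sex-and-site model and report it alongside.
- **Exclusions:** do not put medical mistrust or UBACC in the primary model, because both are measured after exposure.
- **Median fallback:** state whether it carries the same covariates and which contrast it then estimates.

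The cost is up to 3 degrees of freedom, one missing-value rule and, if parental monitoring is used, one scoring rule. No new data are needed.
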